**Table 4. Categories of Tabulation Items for Administration Status**

Item	Category	Note
Total dose [mg]	No category	Continuous data Xeljanz group only
Average daily number of administrations [time/day]	$\leq$ once, $>$ once to $\leq$ twice, $>$ twice to $\leq$ 3 times, $>$ 3 times	Xeljanz group only
Average daily dose [mg]	$\leq$ 5mg, $>$ 5 mg to $\leq$ 10 mg, $>$ 10 mg	Xeljanz group only
	$<$ 7.5mg, $\geq$ 7.5mg	
Average daily number of actual administrations [time/day]	$\leq$ once, $>$ once to $\leq$ twice, $>$ twice to $\leq$ 3 times, $>$ 3 times	Xeljanz group only
Average actual daily dose [mg]	$\leq$ 5mg, $>$ 5 mg to $\leq$ 10 mg, $>$ 10 mg	Xeljanz group only
	$<$ 7.5mg, $\geq$ 7.5mg	
Drugs initially administered	MTX, biological products, DMARDs or immunosuppressants, MTX + biological products, MTX + DMARDs or immunosuppressants, biological products + DMARDs or immunosuppressants, MTX + biological products + DMARDs or immunosuppressants	Control group only  Drugs which are written in “Status of drug administration” within 7 days from the oldest date of commencement

- Tabulation and analysis of each subset

Patient characteristics will be tabulated for each subgroup sorted by the initial daily dose in Xeljanz group (5 or 10 mg). Also, for each subgroup sorted by the initial daily dose, patient characteristics will be further tabulated for new patients started in this surveillance, patients who took part in clinical study, patients transferring from other hospital, subpopulation that meets the MTX criteria, and subpopulation that does not meet the MTX criteria.

Items for which the calculation will be made are shown in “[Appendix 11.1.2 Patient Background](#)”.

### 8.2.3. Safety Analysis

#### 8.2.3.1. Comparison of Xeljanz group and control group

A comparison of the Xeljanz group and the control group is performed for each of the MTX adherent comparative analysis set and the comparative analysis set. The main analysis set is the MTX adherent comparative analysis set.

The adverse events including corporate evaluation is used for the main analysis, and as a secondary analysis, the analysis of adverse events based only on the doctor's evaluation is also used.

#### **8.2.3.1.1. Analysis of malignant tumors**

There are the following 3 definitions for patients with malignant tumors, and the analysis will be performed for each of them. As the primary evaluation, patients with malignant tumors during overall observation period will be used. For other definitions, the incidence of malignant tumor will be calculated, and other relevant analyses will be performed if such result is remarkably different from the data on overall observation period.

- Patients with malignant tumors during overall observation period: Patients with malignant tumors during overall observation period are patients in whom malignant tumors developed from the date of the initiation of treatment to the date of the completion or discontinuation of follow-up.
- Patients with malignant tumors during treatment period: Patients with malignant tumors during treatment period are patients in whom malignant tumors developed from the date of the initiation of treatment to the date of the completion of treatment.
- Patients with malignant tumors during treatment period+28 days: Treatment period will cover 28 days following the completion of treatment; that is, patients to be included in the analysis will be those with malignant tumors developed from the date of the initiation of treatment + 28 days (or not longer than 3 years if the treatment period + 28 days exceeds 3 years).

Other definitions used in the comparison of malignant tumors are shown in [Table 5](#).

**Table 5. Definitions in the Comparison of Malignant Tumors**

Term	Definition
Patients without malignant tumors	Patients who do not correspond to the each definition of patients with malignant tumors
Time to malignant tumor during overall observation period	Date of the development of malignant tumor - date of the initiation of treatment + 1
Censoring period for patients without malignant tumors during overall observation period	Date of completion or discontinuation of follow-up - date of the initiation of treatment + 1
Time to malignant tumor during treatment period	Date of the development of malignant tumor - date of the initiation of treatment + 1
Censoring period for patients without malignant tumors (treatment period)	Date of the completion of treatment - date of the initiation of treatment+ 1
Time to malignant tumor during the treatment period (+28 days)	Date of the development of malignant tumor - date of the initiation of treatment + 1
Censoring period for patients without malignant tumors during the treatment period (+28 days)	Date of the completion of treatment + 28- date of the initiation of treatment + 1

• **Development of malignant tumors**

The number of malignant tumors in each group and the proportion of occurrence are calculated for each SOC and PT. Furthermore, it is calculated for each cancer type (stomach, lung, breast, cervix, uterine body, ovary, malignant lymphoma, large intestine, pancreas, bladder, kidney / urinary tract (excluding bladder), other). Females are targeted for malignant tumors of the breast, cervix, uterine body and ovaries.

• **Incidence rate of malignant tumors**

The number of patients with malignant tumors in each group, incidence rate, and the 95% confidence interval will be calculated in accordance with [Section 8.1.5](#).

In addition, the incidence ratio between treatment groups and the 95% confidence interval and the difference in incidence rate between treatment groups and the 95% confidence interval will be calculated.

For covariates concerning malignant tumors (Section 6.3), incidence by single factor will be calculated, and the pooled incidence ratio and the 95% confidence interval and the pooled difference in incidence rate and the 95% confidence interval will be calculated.

• **Incidence proportion of malignant tumors**

The number of patients with malignant tumors in each group, the incidence proportion, and the 95% confidence interval will be calculated in accordance with [Section 8.1.5](#).

In addition, the ratio of incidence proportion and the 95% confidence interval and the difference in incidence proportion and the 95% confidence interval will be calculated.

For covariates concerning malignant tumors ([Section 6.3](#)), the incidence proportion by single factor will be calculated, and the ratio of the pooled incidence proportion and the 95% confidence interval and the difference in the pooled incidence proportion and the 95% confidence interval will be calculated. Age will be handled as categorical data.

- **Analysis of time to malignant tumor**

Time to malignant tumor in each group will be summarized in accordance with [Section 8.1.4](#). As for the censoring period in patients without malignant tumors, [Table 5](#) will be followed. In addition, a graph showing the transition of the incidence rate estimated using the calculated parameters by applying the Weibull distribution together with the Kaplan-Meier plot, and a graph of the transition of the hazard function are created.

- **Adjusted hazard ratio for the development of malignant tumors**

As for time to malignant tumor, the adjusted hazard ratio of the Xeljanz group to the control group for the development of malignant tumors and the 95% confidence interval will be calculated in accordance with [Section 8.1.5](#). Covariates used for adjustment are shown in [Section 6.3](#).

As for the development of malignant tumors in the Xeljanz group compared to the control group, the propensity score-weighted (inverse probability of treatment weighting, IPTW) hazard ratio and the 95% confidence interval will be calculated. The weight is obtained

from  $Z_i + \frac{\theta_i(1-Z_i)}{1-\theta_i}$  ( $\theta_i$ : the estimated propensity score,  $Z_i$ : 1 (if xeljanz group) or 0 (if control group)). The other propensity score-weighted hazard ratio and the 95% confidence interval also will be calculated from setting an upper limit on the weight, because it is possible that some weights are too high if  $\theta_i$  is nearly equal 1. The upper limit is determined depending on a situation of the estimation accuracy.

In addition to the propensity score-weighted, further adjustment using a model with covariates of large effect will be conducted. The covariates which show large change in adjusted hazard ratio from the non-adjusted hazard ratio in the univariate model, will be included in this model in order to control the number of covariates in the model.

- **Distribution of propensity score and covariates before and after adjustment for hazard ratio of malignant tumor**

The distribution of propensity scores before and after adjustment by weighting of propensity scores is estimated using kernel density estimation and shown by violin plot. In the control group, a boxplot of weights is created.

In addition, the proportion of each category of patient background used for the covariate and the difference between the standardized groups are calculated before and after adjustment. The standardized difference is treated as a continuous amount in the patient background of 3 or more categories, and calculated by the difference / standard deviation of the average value of each group. In the patient background of the binary data, it is calculated by the difference / standard deviation of the ratio of each group. In addition, parameters are calculated in logistic regression model.

- **Standardized incidence rate (SIR) for the development of malignant tumors**

Using the number of malignant tumors in each group, the SIR and its 95% confidence interval with the Japanese as the reference population are calculated according to Section 8.1.6. The expected number of patients is calculated using the population and morbidity by gender and age in 2013.

In addition, the SIR and its 95% confidence interval calculated by using the population and the number of morbidity by gender, age, and calendar year as the expected number of patients are calculated according to Section 8.1.6. If there is no reference population and prevalence in the applicable calendar year, use the reference population and prevalence by gender and age in the latest year.

In addition, SIR is calculated for each cancer type (stomach, lung, breast, cervix, uterine body, ovary, malignant lymphoma, large intestine, pancreas, bladder, kidney / urinary tract (excluding bladder)). Females are targeted for malignant tumors of the breast, cervix, uterine body and ovaries.

Similarly, it is calculated for non MTX adherent safety analysis set.

The Cancer Information of the National Cancer Center Service is used as Japanese population data, and the expected number of patients is calculated using the population and the number of morbidity in the statistical data on cancer.

”.

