- [3] Adverse events leading to death, course of death

Definition of [Malignant tumor]

An event to which definitive diagnosis of malignant tumor (including lymphoma) is given

\*\*"Suspected malignant tumor (including lymphoma)" should also be reported as an adverse event.

Definition of [Serious infection]

Of the infections occurred during this Surveillance, a "serious infection" is defined as an event that;

- [1] Results in or may result in death;
- [2] Results in or may result in disability/incapacity;
- [3] Requires hospitalization or prolongation of existing hospitalization; or
- [4] Is another serious event equivalent to the above.

**Note:** Adverse events are any and all untoward events (including clinically significant abnormal changes in laboratory tests) occurred in subjects after starting Xeljanz treatment regardless of their causal relationship with Xeljanz. Serious adverse events are any untoward medical occurrences that result in death, are life-threatening, require (or prolong) hospitalization, cause persistent or significant disability/incapacity, result in congenital anomalies or birth defects, or are other conditions which represent significant health hazards.

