### **5.1.2. Comparison of the Xeljanz group and the control group**

- Comparative analysis set

Of the enrolled patients with a scheduled observation period of 3 years, those who were confirmed to treat Xeljanz in the Xeljanz group and a control drug (control drug is MTX, biological agents, DMARDs or immunosuppressive drug) at least once were included in the control group. The patients who apply to a to f in Section 5.1.1 are excluded.

The control group also excludes patients who do not meet the MTX criteria and patients who have been treated with Xeljanz.

- MTX adherent comparative analysis set

The MTX adherent comparative analysis set of the Xeljanz group is the patients who meets the MTX criteria among the new patients of the comparative analysis set.

As for the control group, since the comparative analysis set of the control group is limited to the patients who meet the MTX criteria, the same set is also used as the control group of MTX adherent comparative analysis set.

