## **6. ENDPOINTS AND COVARIATES**

### **6.1. Safety Endpoints**

#### **6.1.1. Comparison of Xeljanz group and control group**

- Malignant tumors are tumors with definitive diagnosis among all-causality malignant tumors (including lymphoma).
- Time to occurrence of malignant tumor
- Serious infections are infections corresponding to the following among all-causality infections.
  1. Results in death, or is life-threatening;

2. Results in disability, or may lead to disability;
  3. Requires inpatient hospitalization or prolongation of hospitalization;
  4. Are serious in accordance with the above.
- Time to occurrence of serious infection
  - Death refers to the case where the death column is checked in the status of treatment of Xeljanz (continued or discontinued) or the status of follow-up (continued or discontinued) in the case report form (CRF).

The death was defined to exclude post-survey deaths for comparing fairly in the Xeljanz and control groups, because post-survey deaths are likely to be collected only in the Xeljanz group. However, it was found that there were death cases that were possibly to have been confirmed at the end of the survey and had no reason for discontinuation of the treatment or the follow-up, when the final analysis for the reexamination application (cutoff data on 12/July/2021) was conducted. Since it was found that there were cases that were considered to be high, such cases were exceptionally regarded as cases where the investigation was discontinued due to patient death, and were included in the analysis as cases of death. Such cases were exceptionally regarded as death cases where the survey was discontinued due to death, and were included in the analysis as death cases. The handling of death cases is described in Section 7.

- Time to death

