### 6.3. Covariates

For both the Xeljanz and control groups, candidate covariates related to the development of malignant tumors and serious infections are shown below.

Covariates	Malignant tumor	Serious infection
Sex	○	○
Age	○	○
Weight	○	○
Stage of rheumatoid arthritis	○	○
Class of rheumatoid arthritis	○	○
Duration or disease	○	○
Past history (infection)	×	○
Past history (malignant tumor)	○	×
Past history (lung disorder)	×	○
Past history (interstitial pneumonia)	×	○
Complication (infection)	×	○
Complication (malignant tumor)	○	×
Complication (hepatitis B)	○	×
Complication (hepatitis C)	○	×
Complication (diabetes mellitus)	×	○
Smoking history	○	○
Family history of malignant tumors (including lymphoma)	○	○
History of MTX use (Within 3 months prior to the start of survey)	○	○
MTX criteria	○	○
History of oral steroid use (Within 3 months prior to the start of survey)	○	○
History of tacrolimus use (Within 3 months prior to the start of survey)	○	○
Past use of biological agents (Within 3 months prior to the start of survey)	○	○

Covariats	Malignant tumor	Serious infection
Initial dose of Xeljanz	○	○
Neutrophil count	○	○
Lymphocyte count	○	○
Prophylactic administration to prevent tuberculosis	×	○
Prophylactic administration to prevent pneumocystis jiroveci pneumonia	×	○
Prophylactic administration to prevent hepatitis B	×	○
DAS28	○	○

○: Applicable, ×: Not applicable

Covariates may be added or removed based on the results of the interim analyses of this survey and newly obtained findings. In that case, this plan will be revised.

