#### 8.1.5. Analysis of Incidence Rate and Incidence Proportion of Specified Events

Incidence rate and incidence proportion will be calculated for specified events including initial malignancy, initial serious infection, and death, according to the following formulae.

- **Duration of exposure [patient-year]**

Total of time to each event and time to censoring in each group [day]/365.25

- **Incidence rate amount and the 95% confidence interval**

$$\text{Incidence rate amount [patient/100 patient - years]} = 100 \times \frac{a}{PT}$$

95% confidence interval for incidence per exposure amount [patient/100 patient - years].

$$= \begin{cases} \left[ 100 \times \frac{x^2(0.025, 2a)/2}{PT}, 100 \times \frac{x^2(0.975, 2(a+1))/2}{PT} \right] & (a \neq 0) \\ \left[ 0.00, 100 \times \frac{x^2(0.95, 2))/2}{PT} \right] & (a = 0) \end{cases}$$

a: Number of patients with the event [patient]

PT: Duration of exposure [patient-year]

$x^2(p, d)$ : the lower p quantile for the chi - square distribution with d degrees of freedom

- **Incidence proportion and the 95% confidence interval**

$$\text{Incidence proportion [%]} = 100 \times \frac{a}{N}$$

95% confidence interval for incidence proportion [%]

$$= \left[ 100 \times \left( 1 + \frac{N - a + 1}{aF(0.025, 2a, 2(N - a + 1))} \right)^{-1} \cdot 100 \times \left( 1 + \frac{N - a}{(a + 1)F(0.975, 2(a + 1), 2(N - a))} \right)^{-1} \right]$$

N: Number of patients included in the analysis [patient]

$F(p, m, n)$ : the lower  $p$  quantile for the F distribution with  $m$  and  $n$  degrees of freedom.

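### The SIR for malignant tumors does not exclude recurrence or progression of a cancer present before Day 1, although its expected count is meant to be population incidence of new cancers

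*SAP*

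**What the plan says.** **Observed count.** SAP 8.2.3.1.1 describes the ratio as "Using the number of malignant tumors in each group, the SIR and its 95% confidence interval with the Japanese as the reference population", calculated for all sites and by cancer type. SAP 6.1.1 defines the endpoint: "Malignant tumors are tumors with definitive diagnosis among all-causality malignant tumors (including lymphoma". Protocol 7.6 defines a malignant tumor as "An event to which definitive diagnosis of malignant tumor (including lymphoma) is given". The primary evaluation in SAP 8.2.3.1.1 counts "patients in whom malignant tumors developed from the date of the initiation of treatment to the date of the completion or discontinuation of follow-up". SAP 8.1.5 applies its rate formulas to "specified events including initial malignancy, initial serious infection, and death". None of these texts mentions new primary, recurrence, metastasis or progression.

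**Patients.** For the comparative set, SAP 5.1.2 states: "The patients who apply to a to f in Section 5.1.1 are excluded". Those six reasons are administrative (form, contract, enrollment, missing administration or adverse event information). The further exclusions for controls concern the MTX criteria and Xeljanz use. Past history of malignant tumor and malignant tumor as a complication are not exclusions. Both are candidate covariates for the malignancy endpoint in SAP 6.3.

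**Expected count.** The tables in SAP 8.1.6 label the reference rate an incidence rate, cases divided by population. One version is stratified by sex and age, the other also by calendar year. Reference 8 of the SAP points to a national file of cancer incidence. In SAP 8.2.3.1.1, however, the sentence on missing calendar years calls the reference figure prevalence. That section also speaks of the number of tumors, whereas the 8.1.6 tables count patients.

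**The concern.** An SIR is interpretable only if the numerator and the reference rate count the same kind of event. National incidence counts newly diagnosed cancers. If the survey also counts the return or spread of a cancer diagnosed before Day 1, the observed count contains events that the expected count cannot contain. Covariate adjustment for earlier cancer exists only in the between-group analyses; the SIR is standardized for sex, age and, in one version, calendar year.

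Malignancy is a named objective of the survey, and the SIR is the SAP's visible comparison of malignancy with the general population. An SIR above 1 could then partly reflect recurrences. If the share of patients with earlier cancer differs between groups, the two SIRs could differ for that reason alone.

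**Working it through.** **1. Could a recurrence meet the event rule?** The Protocol 7.6 note states: "Adverse events are any and all untoward events (including clinically significant abnormal changes in laboratory tests) occurred in subjects after starting Xeljanz treatment". A relapse confirmed after Day 1 fits that definition and can carry a definitive diagnosis. Two words might narrow it:
- *Developed* is also used in the SAP for serious infections (8.2.3.1.2) and for deaths (8.2.3.1.3), so it marks onset within a window.
- *Initial* malignancy stands beside initial serious infection. Past infection is a covariate for that endpoint (SAP 6.3), so first in the survey is the natural reading.

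Neither word is defined and neither is a new-primary rule. A relapse is therefore not excluded, but no text says it is included.

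**2. The plan's own figure.** The documents state no SIR, observed count or expected count for the survey. The nearest figure is 104 patients with a malignant tumor among 4000 (Protocol section 3). Inputs: 1.16 per 100 person-years, 3 years, about 50% dropout. With linear loss:
- person-years = 4000 × (0.5 × 3 + 0.5 × 1.5) = 9000
- events = 9000 × 0.0116 = 104.4, which reproduces 104.

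**3. Effect by share and recurrence rate (both assumed).** Let p be the share of patients with past or current cancer and r the rate of counted recurrences. Take 1.16 per 100 person-years as the new-primary rate; this too is an assumption, because the protocol says only malignant tumor. Added events = p × 9000 × r. The SIR is multiplied by 1 + p × r / 0.0116, whatever the expected count and person-years.

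| p | r per 100 person-years | Added events | SIR multiplied by |
|---|---|---|---|
| 0 | any | 0 | 1.00 |
| 1% | 1 | 0.9 | 1.01 |
| 3% | 5 | 13.5 | 1.13 |
| 5% | 5 | 22.5 | 1.22 |
| 5% | 10 | 45.0 | 1.43 |

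**4. Effect on the interval.** Fix the observed count at D = 104, of which R are recurrences, and let the true new-cancer SIR be 1.00, so E = 104 − R. The reported SIR is 104 / (104 − R), with the chi-square limits of SAP 8.1.6:

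| R | E | Reported SIR | 95% CI |
|---|---|---|---|
| 0 | 104 | 1.00 | 0.82–1.21 |
| 2 | 102 | 1.02 | 0.83–1.24 |
| 5 | 99 | 1.05 | 0.86–1.27 |
| 10 | 94 | 1.11 | 0.90–1.34 |
| 21 | 83 | 1.25 | 1.02–1.52 |

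In the last row the interval lies above 1 although the true ratio is 1.00. Small values of R disappear in sampling error.

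**The case against.** The strongest reply is that the counting of recurrences is inferred from silence. Progression of a tumor diagnosed before Day 1 does not plainly fit an event to which a diagnosis is given, and the SAP records existing tumors separately as a baseline item. SAP 6.1.2 refers to a procedural manual for extracting key survey items. The revision history mentions a sensitivity section 8.2.3.1.4 that is not visible. Either might address the matter. This stands in part: inclusion is not shown, and those texts cannot be judged. The visible SIR rule is nonetheless open, and a programmer would have to decide.

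A reader might infer that the SIR *is* biased upward. The documents do not support that. The effect is zero if no such event is counted. If prevalence really were used for the reference rate, the expected count would be too large and the SIR too low. Upward describes this one mechanism; the net direction stays open until the wording is corrected.

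A reader might also infer that simply dropping patients with earlier cancer gives the right SIR. It does not quite: it also removes their new primaries, while the reference population is not restricted to cancer-free people. Nor do the documents show that the site-specific SIRs suffer most, because that depends on which cancers recur.

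Finally, all tests are exploratory (SAP section 4), the hazard ratios use both history items as covariates, and malignancy incidence is to be calculated by each single covariate. This limits the consequence, but none of it yields an SIR matched to its reference.

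**Conclusion.** The point holds conditionally. As written, the SIR numerator does not exclude recurrence, metastasis or progression of a cancer present before Day 1, patients with such histories remain in the set, and the comparator is meant to be incidence of new cancers. To the extent such events are counted, the SIR is pushed upward. The size cannot be determined from the documents. The range from no effect to about +43% rests wholly on assumed shares (0 to 5%), assumed recurrence rates (up to 10 per 100 person-years) and 1.16 per 100 person-years as the new-primary rate. Counting several tumors in one patient, which the text of 8.2.3.1.1 permits and the 8.1.6 tables do not, would be a separate upward push. This is a cheap improvement to one analysis and does not undermine the between-group comparison.

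**What to change.** In SAP 8.2.3.1.1:
- Define the SIR event as the first new primary malignant tumor diagnosed after Day 1, one per patient, excluding recurrence, metastasis or progression of a tumor present before Day 1.
- Replace prevalence with incidence for the reference figures.
- As a sensitivity analysis, and wherever new and recurrent tumors cannot be told apart, also calculate the all-site and site-specific SIRs after removing patients with past history of malignant tumor or malignant tumor as a complication from both events and person-years. State that the reference population is not so restricted.
- Keep the all-patient SIR as a labelled supplement.

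**Cost.** The change needs a few sentences and one filter on clinical history, which Protocol 7.1 records for both groups. The new-primary definition also requires each event to be classified from the diagnosis and detailed tumor information under Protocol 7.6; no dedicated new-or-recurrent item is shown, which is why the restricted SIR is needed as a fallback. Events and person-years fall slightly, so intervals widen slightly. SAP version 10.0 already postdates the database release, so the new SIRs should be marked as added after that point.
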